ABR	General Assessment and Registration form (ABR form), the application form that is required for submission to the accredited Ethics Committee; in Dutch: Algemeen Beoordelings- en Registratieformulier (ABR-formulier)
AE	Adverse Event
AR	Adverse Reaction
CA	Competent Authority
CCMO	Central Committee on Research Involving Human Subjects; in Dutch: Centrale Commissie Mensgebonden Onderzoek
CV	Curriculum Vitae
DSMB	Data Safety Monitoring Board
EU	European Union
EudraCT	European drug regulatory affairs Clinical Trials
GCP	Good Clinical Practice
GDPR	General Data Protection Regulation; in Dutch: Algemene Verordening Gegevensbescherming (AVG)
IB	Investigator's Brochure
IC	Informed Consent
IMP	Investigational Medicinal Product
IMPD	Investigational Medicinal Product Dossier
METC	Medical research ethics committee (MREC); in Dutch: medisch-ethische toetsingscommissie (METC)
(S)AE	(Serious) Adverse Event
SPC	Summary of Product Characteristics; in Dutch: officiële productinformatie IB1-tekst
Sponsor	The sponsor is the party that commissions the organisation or performance of the research, for example a pharmaceutical company, academic hospital, scientific organisation or investigator. A party that provides funding for a study but does not commission it is not regarded as the sponsor, but referred to as a subsidising party.
SUSAR	Suspected Unexpected Serious Adverse Reaction
UAVG	Dutch Act on Implementation of the General Data Protection Regulation; in Dutch: Uitvoeringswet AVG
WMO	Medical Research Involving Human Subjects Act; in Dutch: Wet Medisch-wetenschappelijk Onderzoek met Mensen

SUMMARY

Rationale: To determine the plasma lycopene concentration before and after an oral intake of lycopene in order to use this measurement as a life style compliance marker.

Objective: Primary objective: to determine if a plasma lycopene concentration can serve as a response parameter after a single dose of dietary lycopene.

Study design: Cross-over interventional pilot study.

Study population: Ten male healthy volunteers 18-75 years.

Intervention: Oral food supplement tablet 40 mg lycopene once, versus oral soup of cooked tomatoes equivalent to 40 mg lycopene content. In addition, the participants' habitual diet and actual food intake during the intervention will be measured using a food frequency questionnaire and a food diary.

Main study parameters/endpoints: Variation of plasma lycopene 1 hour before, and 1,3,6,12,24,48,72 hours after intervention.

Nature and extent of the burden and risks associated with participation, benefit and group relatedness: Eight blood samples of 6 ml full venous blood obtained by vena

puncture per intervention per individual, 2 times in a cross-over pilot study, in which interventions are 3 weeks apart (so 2 x 8 samples in 10 volunteers). Risk of vena puncture is negligible, idemque the burden.

1. INTRODUCTION AND RATIONALE

Dietary study in Prostate cancer: Men with prostate cancer (PCa) often ask if the (composition of) their diet may contribute to the suppression of their tumor. There is indirect epidemiological evidence that diet, especially antioxidants like lycopene, are beneficial for an advantageous course of PCa [1]. Lycopene is a non-provitamin A carotenoid that exhibits several health benefits. Epidemiological data support a correlation between lycopene intake and the attenuation of several chronic diseases, including certain types of cancers and cardiovascular diseases. It is currently unknown whether the beneficial effects are from the native structure of lycopene or its metabolic derivatives [2].

Scientific proof for the impact of dietary interventions on PCa growth is extremely difficult to provide, as the natural course of PCa from the time of diagnosis is frequently over 20 years. In dietary studies many confounders are present, therefore dietary studies also need extreme large populations. Furthermore, the biochemical parameters needed to study lycopene concentrations in blood do not have defined normal values: SNPs in *BCO1* and other genes may modulate human plasma and prostate tissue responses to dietary lycopene intake. These individual genetic variants related to carotenoid metabolism may partially explain heterogeneous human blood and tissue responses and may be critical covariates for population studies and clinical trials [3]. On top of that, intestinal absorption is promoted by co-consumption of fat [2], and 10 gram of olive oil has been identified as an optimal dose for lycopene uptake. The way lycopene itself is offered appears to be less of importance, as there was no difference of plasma concentration observed between well processed dietary and artificial in-tablet servings of lycopene [4].

While the generally accepted opinion is that diets high in antioxidants are beneficial for suppressing and prevention of all cancers, and that they promote the overall health status of individuals, it may be difficult to change a life style that incorporates a healthy diet. Therefore in this study, we are searching for a parameter in body fluids that reflects the intake of healthy diet, and as such may motivate and sustain its continuous use (compliance marker). In case of prostate cancer we address lycopene as our target for reasons described above. Ideally, our lycopene related marker should reflect the short-term uptake of lycopene, and be based on a single dose consumption, in order to act as a direct feed-back to the consumers dietary action. Current methods of determination (see further) do not yet live up to point-of-care applications. There is, however, evidence that single dose consumption is reflected in the lycopene plasma concentration. In a trial in Italian consumers on lycopene kinetics on single dose consumption [5], a significant increase of plasma lycopene concentration of 40

nmol/l was observed above an individual base level (around 400 nmol/l), with a max concentration at 12 hours, and a normalisation after 48 hours after consumption of 15 mg of lycopene. Also a biomarker reflecting the adequate lycopene consumption of a medium long term (e.g. one week consumption) might provide a valuable asset for consumers. In a trial in Swiss male consumers on an 8-day intervention of 20 mg after lycopene depletion, the individual lycopene plasma concentration topped to a steady state of 1000 to 1500 nmol/l, while two weeks after the intervention (so during lycopene depletion) a plateau phase was obtained on a plasma concentration of 400-500 nmol/l [4], likely due to the release of lycopene from liver resources. We conclude that for consumer reasons the choice for a point-of-care testing of single dose lycopene is feasible, but restricted by current technology, and that feed-back on medium long term lycopene consumption is also feasible, as it is well reflected in plasma lycopene concentrations.

Study design: We have chosen lycopene as it is related to PCa growth, it can be used as a dietary intervention, and it is measurable reproducibly in food and in body fluids. Here we study the lycopene plasma concentration dynamics after a single dose consumption in volunteers in a Dutch setting (which differs from the geographic and environmental setting and life-style in the above mentioned studies). This is to obtain the necessary information on technology, logistics, and food products needed to conduct the follow-up study (METC 2017-389) in cancer patients. Once we have proven that a measurable response can be obtained in healthy volunteers in a Dutch population, that the assay is available and robust, and in line with food consumption as evaluated by validated food questionnaires, we will incorporate that parameter (lycopene) in the current randomised study for men with PCa and undergoing treatment or have undergone treatment in the past in which three dietary interventions are given and compliance to the intervention is currently measured by food intake questionnaires (METC 2017-389).

Here we test plasma lycopene as a candidate compliance marker for that purpose. This is based on the assumption that in Dutch participants the plasma level of lycopene might be comparable to the Swiss population literature, that a single dose response to 40 mg lycopene in combination with oil will provide a measurable response of plus 10 % in individuals, and that a concentration between 1000-1500 nmol/l is appreciated by patients and caregivers as the optimal lycopene plasma concentration to be accomplished long term (1-3 months).

Dietary interventions should always be analysed against the background of the normal individual diet. Therefore, to evaluate the lycopene intervention and related marker, it is

crucial to take the participant's habitual diet, as well as actual food intake during the intervention into account [6].

Research questions:

- 1) Can a plasma lycopene concentration serve as a response parameter after a single dose of dietary lycopene.

We will measure plasma carotenoid concentrations (including lycopene) in response to a single dose dietary intervention with lycopene-rich food or a lycopene tablet in a cross-over study design.

Plasma lycopene concentrations show variation between individuals, and within individuals. It is unknown if and how much a single dietary intervention with lycopene from lycopene-rich vegetables like tomatoes alters the plasma concentration, and therefore can be used as a compliance marker.

As the bioavailability and plasma kinetics of lycopene is known to a limited extend (see studies above), a scheme for plasma determinations is followed according to previous marker (GABA, also found in tomatoes, serving as an exemplary study design) research from the same Wageningen group, including a wash out period of at least two weeks between interventions in the cross-over design [7].

- 2) Is a tablet lycopene with equivalent lycopene content as effective as a single dose dietary intervention regarding the change of plasma lycopene concentration?

Previous studies suggest equivalence, which might be of interest for consumers/patients.

- 3) Is the prior food consumption of individuals, as measured by dietary questionnaires, related to the plasma lycopene levels before and after lycopene intervention?

If an existing individual high intake of lycopene as analysed by a validated questionnaire would result in a high standard plasma lycopene concentration, or little response on single dose lycopene consumption, the subject might exclude for further supplementary lycopene consumption and life style changes.

Intervention: We have chosen a single dose of 40 mg lycopene as an intervention based on the following. Previously, in a dose escalating study to 90 mg lycopene daily in men with Research protocol

recurrent PCa after primary treatment, no effects were seen on the level of PSA, in contradiction to two studies conducted in men with metastatic PCa [8]. Also in high doses maintained for several weeks no toxicity was observed, while lycopene plasma levels corresponded with dietary dose. For chronic use, the daily dose of 30 mg is recommended based on a large review [9].

Lycopene belongs to the chemical family of carotenoids that can be found in intensely coloured fruits and vegetables, like tomatoes. The uptake from the alimentary tract is increased by heating the natural present lycopene, initiating a chemical conversion from a trans to a cis-form [10]. Uptake of lycopene and its geometrical isomers is greater from heat-processed than from unprocessed tomato juice in humans [10]. The addition of oils also are reported to have a beneficial influence [11]. Lycopenes are absorbed in the gut, and transported in chylomicrones because of their lipophylic nature [12]. Their exact biological action is still unknown, but regarded to be an antioxidant.

Various dietary interventions have been applied previously for the study on bioavailability of lycopene. The lycopene content in 200g of tomato soup equals ca.33 mg of lycopene. Most experimental studies aim to provide 40 mg lycopene whether in a carotene-rich diet, whether by pill-form (supplement), in combination with a minimum of 10 g of fat [2].

Assay: Standard liquid-chromatography-based technology for the analysis of carotenoids and similar structures including lycopene. Plasma carotenoids, including retinol, alpha- and beta-carotene, beta-cryptoxanthin, lutein, lycopene, tocopherols and zeaxanthin, are determined using ultra-pressure liquid chromatography coupled to diode array detection (UPLC-DAD). In short, 375 µL plasma is denatured using ethanol in the presence of the internal standard retinyl acetate. The carotenoids are subsequently extracted using 0.01% w/v butylated hydroxytoluene in hexane. The extracts are dried under nitrogen in a TurboVap evaporator (Biotage, Uppsala, Sweden) at 35 °C, reconstituted in acetonitrile, and transferred to a LC vial. LC analysis is performed on a Acquity H-class UPLC coupled to an Acquity PDA eLambda detector (Waters, Etten-Leur, the Netherlands) using an Acquity UPLC HSS T3 column (Waters). Gradient elution is performed using a mixture of acetonitrile-dichloromethane-methanol (ratio 85:5:10) containing 0.1% ammonium acetate (eluens A) and ULC-MS grade water (eluens B) with a constant flow of 400 µL/min and a runtime of 30 min. The detector is set at 292, 325 and 450 nm. Concentrations are calculated using a 6-point calibration curve. A pooled plasma sample is analyzed in duplicate in each analytical batch to monitor the quality of the analyses.

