4.4 Sample size calculation

Observational study obtaining individual lycopene concentration curves in plasma. It is anticipated that a measurable lycopene response will be seen in all participants. Based on the literature described in the introduction section it is hypothesized that in Dutch participants the plasma level of lycopene might be comparable to the Swiss population, that a single dose response to 40mg lycopene in combination with oil will provide a measurable response of plus 10% in all individuals. Therefore a sample size of two times five participants (10 participants in total) has been chosen.

Our pilot still needs to obtain an impression that responses are observed in all individuals, and to confirm that our HPLC-assay is an adequate technique. We will express that in

percentages of the group, such as: 'In xx percent the lycopene concentration increased more than 10% of the T=0 within 48 hours after intervention A'.

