10.1 Primary study parameter(s)

Lycopene plasma concentration curves over time will be depicted in tables and in graphs in absolute and relative (compared to T0) amounts. Trends in changes over time will be interpreted, if needed based on background information on confounding parameters. There are no statistical calculations planned.

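### The only numerical criterion is a rise over a T0 drawn one hour before the dose; it shows uptake, not that a sample without that reference can serve as a single-dose compliance marker

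*Protocol*

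**What the plan says.** Section 1 (Study design) sets three conditions for taking lycopene into the randomised study METC 2017-389. The first is a response: "Once we have proven that a measurable response can be obtained in healthy volunteers in a Dutch population". The other two are "that the assay is available and robust, and in line with food consumption as evaluated by validated food questionnaires". If they are met, "we will incorporate that parameter (lycopene) in the current randomised study for men with PCa". Research question 1, also in section 1, moves directly from an altered concentration to usability as a compliance marker.

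Only the response is given a number, in section 4.4, where the result is to be worded as "In xx percent the lycopene concentration increased more than 10% of the T=0 within 48 hours after intervention A". No required percentage is named. Section 3 places T0 one hour before the intervention, and section 8.1.1 defines the main endpoint as the rise, absolute and as a percentage of T0. Section 10.1 plans tables and graphs in "absolute and relative (compared to T0) amounts" and rules out any statistical calculation. Section 10.2 limits the FFQ and diary data to description.

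Section 1 also states that "Plasma lycopene concentrations show variation between individuals, and within individuals" and that "the biochemical parameters needed to study lycopene concentrations in blood do not have defined normal values".

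**The concern.** A rise over a man's own value from one hour earlier answers whether a dose reaches the plasma. A compliance marker has to answer something else: given the reference available at the check, can men who took lycopene be told from men who did not? A same-day T0 removes the between-man and longer-term within-man variation that the protocol acknowledges. That variation decides the second question if the check has only an older baseline, or none.

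At stake is a decision about a running randomised study. A high responder percentage could be read as support for the marker although nothing planned in the pilot quantifies separation without T0. The other two conditions offer little protection, because neither has a threshold. The FFQ validation described in section 8.3 does not name lycopene.

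**Working it through.** **Inputs from the protocol.** The Italian single-dose trial cited in section 1 found a rise of 40 nmol/l on a base of about 400 nmol/l after 15 mg. The Swiss trial cited there gives 400-500 nmol/l during depletion and 1000-1500 nmol/l at steady state after 8 days of 20 mg. Sections 1 and 4.4 assume a 10% response to 40 mg. There are 10 men, two periods and 8 samples per period.

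**Inputs assumed.** The protocol gives no SD. I take a between-man CV of 20% to 60% and a within-man CV of 10% to 20%. Linear scaling of the rise from 15 to 40 mg is also an assumption.

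**1. The plan's own figures.** 40/400 = 10%, which matches the assumed response. 10 × 2 × 8 = 160 samples, which matches section 3. The sample size of 10 has no alpha, power or SD behind it, so there is nothing to reproduce.

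**2. Overlap without any assumed CV.** 400 + 40 = 440 nmol/l, the limiting case of the criterion, lies inside 400-500 nmol/l. The width of that range, 100 nmol/l, is 100/40 = 2.5 times the rise. (The two figures come from different trials.)

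**3. One sample, no T0.** Let the base be lognormal with σ = √ln(1 + CV²), and let every man rise by the same proportion r. The AUC is the chance that a random post-dose value exceeds a random undosed value from another man: AUC = Φ(ln(1 + r) / (√2 · σ)).

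For r = 10%, ln 1.10 = 0.0953. Linear dose scaling gives 40 × 40/15 = 106.7 nmol/l, so r = 106.7/400 = 26.7%.

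| Between-man CV | AUC, rise 10% | AUC, rise 26.7% |
|---|---|---|
| 20% | 0.63 | 0.80 |
| 30% | 0.59 | 0.72 |
| 40% | 0.57 | 0.67 |
| 60% | 0.55 | 0.62 |

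Example: at CV 20%, σ = √ln 1.04 = 0.198, and 0.0953/(1.414 × 0.198) = 0.34, so Φ = 0.63. In the 26.7% column every man exceeds 10% over his own T0, so a responder rate of 100% goes with an AUC anywhere from 0.80 to 0.62. A 10% rise is the limiting case, and values just above it give practically the same AUC.

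**4. Own baseline, but an old one.** With independent within-man variation at both samples, AUC = Φ(ln(1 + r) / (2σ_w)). For r = 10% this is 0.68 at a within-man CV of 10% and 0.60 at 20%. For r = 26.7% it is 0.88 and 0.73.

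**5. What ten men can estimate.** For an AUC of 0.60 with 20 against 20 values treated as independent, the Hanley-McNeil SE is √[(0.24 + 19 × 0.0686 + 19 × 0.09)/400] = 0.09. The 95% interval is about 0.42 to 0.78. The values are repeated within men, so this is only a guide.

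**The case against.** The strongest reply is that the stated objective in section 2 is modest: whether plasma lycopene can be a response parameter after one dose. A T0-based read-out in a ten-man pilot fits that. Incorporation formally needs all three conditions. Research question 3 relates habitual intake to levels before and after dosing, which is a between-man question. Absolute values get the same tables and graphs as relative ones, so a careful reader will see both T0 values and their overlap with post-dose values. All of this stands. What is missing is a summary of separation and a statement of how it bears on the decision.

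Three stronger readings are tempting and should not be drawn.

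- A reader might infer that a perfect responder result alone releases the marker. Section 1 asks for more, even if the other conditions have no threshold.
- A reader might infer that the follow-up study will have no usable baseline, or that the marker cannot work there. Its sampling scheme is not in the document. For sustained intake the quoted ranges, 1000-1500 against 400-500 nmol/l, do not overlap, so an absolute level might separate well. This single-dose pilot does not test that.
- A reader might combine a fixed 40 nmol/l rise for every man with a universal response. On bases spread symmetrically around 400 nmol/l, a fixed 40 exceeds 10% only where the base is below 400, in about half the men. Ten of ten would then have probability 0.5¹⁰, about 0.1%. The AUCs above therefore use a proportional rise.

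**Conclusion.** The concern holds for the single-dose marker. The one numerical criterion shows uptake, and no planned read-out measures separation without an immediate pre-dose sample. The overlap of 440 nmol/l with the 400-500 nmol/l depletion range rests on the protocol's own figures. The AUCs of 0.63 to 0.55 for a 10% rise and 0.80 to 0.62 for a 26.7% rise rest on assumed CVs, a proportional rise and, for the latter, linear dose scaling. They show what is possible, not what will be found. How much this matters in use depends on the reference available in METC 2017-389, which the protocol should state.

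**What to change.** In section 10.1, replace the statement that rules out calculations with three descriptive read-outs:

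- (a) the between-man and within-man SD of the 20 T0 values (two per man, about three weeks apart);
- (b) at each post-dose time, the overlap or AUC of absolute post-dose values against T0 values, with an interval that allows for repeated samples per man;
- (c) the period-2 response re-expressed against the period-1 T0, beside the same-day version.

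In section 1, state which reference METC 2017-389 will have (an own earlier baseline, or none). Say that the matching read-out, (b) or (c), will be weighed in the decision to incorporate. Add that the responder percentage against a same-day T0 shows uptake and is not by itself evidence of a usable compliance marker.

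The cost is one extra table and a few sentences, with no new samples or visits. Three limits should be stated. Men keep their normal diet (section 5.2), so T0 means no study dose rather than no lycopene. Read-out (c) has ten values, five per product. With ten men the estimates are too imprecise to act as a strict pass/fail gate.

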2. OBJECTIVES

Primary Objective:

To determine whether a plasma lycopene concentration can serve as a response parameter after a single dose of dietary lycopene.

Secondary Objectives:

1. To determine if a food supplement tablet lycopene with equivalent lycopene content compared to a single dose dietary intervention provides identical plasma lycopene concentration responses compared to the dietary intervention.
2. To determine the influence of prior food consumption, as measured by dietary questionnaires, on plasma lycopene levels before and after lycopene intervention.

3. STUDY DESIGN

Cross-over interventional pilot study.

Ten healthy individuals (male 18-75 years) are randomly divided in two groups (A and B) of 5 individuals. One week before the dietary intervention a daily food questionnaire will be completed.

One hour before the intervention a blood sample will be taken (all blood samples 6 ml EDTA plasma tube). All individuals will be given an infusion needle for 26 hours. Samples are spun and plasma is pipetted and distributed over 1 ml Eppendorf cups for immediate freezing at -80 Celsius at the research lab.

Group A will take 40 mg lycopene (2,5 pills of food supplement Vitabiotics Ultra Lycopene 15mg, potent extract). Group B will take 250 ml of tomato soup (matching with 40 mg lycopene) with 20 ml olive oil. Blood sampling as described in all individuals from needle: 1,3,6,12,24 hours after intervention, and after 48 and 72 hours by direct venapunction. Wash out period of 3 weeks, after which the identical above procedure takes place including questionnaires, but group A and B changed (cross-over). All samples (n=160) will be frozen at -80, and transported on dry ice to Wageningen University for lycopene determination.

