5. TREATMENT OF SUBJECTS

5.1 Investigational product/treatment

Intervention 1: 40 mg lycopene (i.e. 2.5 food supplement pills of Vitabiotics Ultra Lycopene 15mg, potent extract). Tablets contain 430mg Tomato Extract which provides 15mg pure Lycopene, no artificial colours or preservatives, made by Vitabiotics, UK.

Intervention 2: 250 ml of tomato soup with 20 ml olive oil. Soup will be prepared from 5 kg freshly harvested tomatoes (Harvest of Health lycopene enriched tomato), blended, and frozen down at -20 C for max 1 week. These tomatoes have been characterised previously on their lycopene content which will be determined again at Wageningen University Human Nutrition Research Unit of Wageningen University and Research.

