6. INVESTIGATIONAL PRODUCT

6.1 Name and description of investigational product(s)

Food supplement Vitabiotics Ultra Lycopene 15mg, potent extract. Tablets contain 430mg Tomato Extract which provides 15mg pure Lycopene, no artificial colours or preservatives, made by Vitabiotics, UK.

Tomatoes are a source of bioactive phytochemicals and are widely consumed. The phytochemical pattern of tomato products can be refined by choosing breeds with naturally higher nutrient levels that require more intense horticultural techniques and food processing [13]. Producing high-nutrient tomatoes is achieved through classic and conventional breeding techniques, done by professional vegetable breeding companies, as indicated in European Union Law. This process does not include genetic modification processes. In this study the Harvest of Health (Proudesse) tomato will be used. Per 100g this tomato contains 8,4mg lycopene, which is three times higher as 'normal' supermarket tomatoes. Unique characteristics of the Proudesse tomato are its preservability, shape, high concentration of lycopene and its taste.

Per subject 250 ml of tomato soup with 20 ml olive oil will be prepared from freshly harvested Harvest of Health lycopene enriched tomatoes, blended, and frozen down at -20 °C for max one week.

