6.4 Summary of known and potential risks and benefits

Food supplement Vitabiotics Ultra Lycopene, 15mg, potent extract: according to the manufacturers' frequently asked questions page 'Ultra Lycopene has no known side-effects when taken as directed' (<https://www.vitabiotics.com/products/ultra-lycopene-tablets>).

Harvest of Health tomato: the Harvest of Health tomato contains 8,4mg lycopene per 100gr. The acceptable daily intake of lycopene is 0,5 mg/kg bodyweight. For an average male participant weighing 80kg this would result in consuming a maximum of 40mg lycopene per day, converting into a daily uptake of \pm 500gr of tomatoes. It is not likely that participants will eat more than 500gr of tomatoes per day and therefore the risk of consuming too much lycopene is low.

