8.3 Study procedures

Participants will be randomized into the study scheme AB versus BA (cross-over). One week before the intervention a food frequency questionnaire will be distributed to participants. Group A will take 40mg lycopene (2,5 pills of food supplement Vitabiotics Ultra Lycopene 15mg, potent extract). Group B will take 250 ml of tomato soup (matching with 40mg lycopene) with 20ml olive oil. Wash out period of 3 weeks, after which the identical procedure takes place including questionnaires, but group A and B changed (cross-over).

Blood draws are taken on indicated time points (before intervention, 1, 3, 6, 12, 24, 48 and 72 hours after intervention) in standard vacutainers (BD Vacutainer; Becton, Dickinson and Company). For the first blood draws (before intervention and 1-24 hours

after the intervention) all participants will be given an infusion needle for 26 hours. Blood draws after 48 and 72 hours will be done by direct venapunction. Next, the tubes are centrifuged at 3000g for 10 minutes at 4 °C (Sigma 4-16K; Sigma-zentrifugen). Plasma samples are immediately put on dry ice for rapid freezing. At the end of each test day, the plasma samples are stored at -80 °C until further analysis.

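### By the protocol's own tomato content, 250 ml of soup made as written holds about 21–22 mg lycopene, not 40 mg; the roughly 1.9-fold concentration that would close the gap is stated nowhere

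*Protocol*

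**What the plan says.** The soup portion and its dose are fixed together in two places: "Group B will take 250 ml of tomato soup (matching with 40 mg lycopene) with 20 ml olive oil" (section 3) and "Group B will take 250 ml of tomato soup (matching with 40mg lycopene) with 20ml olive oil" (section 8.3). The comparator is 2.5 tablets of 15 mg, also described as 40 mg.

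The composition of the study tomato is in section 6.1: "Per 100g this tomato contains 8,4mg lycopene". Section 6.4 uses the same content to derive a safe intake. For an 80 kg man "this would result in consuming a maximum of 40mg lycopene per day, converting into a daily uptake of" about 500 g of tomatoes.

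On preparation, section 5.1 says "Soup will be prepared from 5 kg freshly harvested tomatoes (Harvest of Health lycopene enriched tomato), blended, and frozen down", with storage limited as "frozen down at -20 C for max 1 week". Section 6.1 repeats the blending and freezing, and section 6.8 adds warming to about 60–80 °C for serving. The Summary calls the tomatoes cooked. Section 5.1 also has the tomatoes' lycopene content measured again before use.

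On timing, section 3 says "Wash out period of 3 weeks, after which the identical above procedure takes place", with the two groups of five exchanged.

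Secondary objective 1 (section 2) asks whether "a food supplement tablet lycopene with equivalent lycopene content compared to a single dose dietary intervention" gives the same plasma response. Research question 2 in the Introduction asks the same.

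**The concern.** Two statements about the soup cannot both be true of the preparation described. Section 6.4 needs about 500 g of this tomato for 40 mg, while sections 3 and 8.3 claim 40 mg in 250 ml. Blending, freezing and warming leave the lycopene per gram unchanged.

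The tablet-versus-soup comparison presupposes equal doses. If the soup carries about half the intended dose, the imbalance goes with the treatment in every participant, and the cross-over does not remove it. Section 10 plans only tables and graphs, so readers would judge the curves by eye with no allowance for dose. If the tomato mass in each portion is not recorded, the true dose cannot be recovered afterwards.

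**Working it through.** **Inputs**
- Tomato content c = 8.4 mg/100 g = 0.084 mg/g (section 6.1).
- Portion 250 ml, claimed dose 40 mg (sections 3 and 8.3).
- Tablets: 2.5 × 15 mg = 37.5 mg (sections 3 and 5.1).
- Tomatoes bought: 5 kg; ten men each take soup once, five per period (sections 3 and 5.1).
- Soup density d = 1.00–1.05 g/ml. This is an assumption; the protocol gives none.

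**Trying to reproduce 40 mg in 250 ml**

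| Reading | Arithmetic | Lycopene per portion |
|---|---|---|
| Soup as written, d = 1.00 | 250 × 1.00 × 0.084 | 21.0 mg |
| Soup as written, d = 1.05 | 250 × 1.05 × 0.084 | 22.1 mg |
| 20 ml oil counted inside the 250 ml, d = 1.00 | 230 × 0.084 | 19.3 mg |
| Introduction's tomato soup, 33 mg per 200 g | 33/200 × 250 | 41.3 mg |
| 5 kg is the total for ten portions | 5000/10 × 0.084 | 42.0 mg |
| 5 kg is one batch for five men, all used | 5000/5 × 0.084 | 84.0 mg |

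The claimed 40 mg is close to the fourth and fifth rows. The fourth row's soup has 33/2 = 16.5 mg per 100 g, about twice the content of the study tomato. The fifth row puts 500 g of tomato into 250 ml, which needs a reduction that is not described.

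**Size of the shortfall**
- Share of the stated dose: 21.0/40 = 53% to 22.05/40 = 55%.
- Concentration needed: 40/21.0 = 1.90-fold to 40/22.05 = 1.81-fold.
- Tomato needed: 40/0.084 = 476 g for 40 mg; 37.5/0.084 = 446 g to match the tablets.
- Unreduced volume for 40 mg: 476/1.05 = 454 ml to 476/1.00 = 476 ml.
- Tablet-to-soup dose ratio: 37.5/22.05 = 1.70 to 37.5/21.0 = 1.79.

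**Can the mass per portion be read from the 5 kg?** Soup is kept at most one week and the periods are three weeks apart, so at least two batches are needed. The text does not say whether 5 kg covers both or is bought for each.

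**Illustration of the effect on plasma response.** The Introduction reports a rise of 40 nmol/l after 15 mg, from a base of about 400 nmol/l. Assume equal uptake from both forms, and a rise that is either proportional to dose or proportional to its square root.
- Proportional: tablets 40 × 37.5/15 = 100 nmol/l; soup 40 × 21/15 = 56 nmol/l; ratio 1.79.
- Square root: tablets 40 × √2.5 = 63 nmol/l; soup 40 × √1.4 = 47 nmol/l; ratio 1.34.
- With 22.05 mg in the soup the ratios are 1.70 and 1.30.

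Against the 10% response threshold in section 4.4, 21 mg gives 56/400 = 14% or 47.3/400 = 12% at a base of 400 nmol/l. At 500 nmol/l it gives 11% or 9.5%.

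**The case against.** The strongest reply is that the soup is meant to be cooked down. The Summary speaks of cooked tomatoes and names 40 mg as the dose. Five kilograms over ten men is 500 g, or 42 mg, each, which agrees with section 6.4. The Introduction's soup also cannot be plain blended tomato: if the study tomato has three times the normal content, a normal one has 8.4/3 = 2.8 mg per 100 g, and that soup has 16.5/2.8, about six times as much. On this reading the fault is an unwritten recipe step, not a proven under-dose. This is plausible and stands as far as it goes. But a near twofold reduction determines the dose, and someone following the protocol as written would not perform it. The 84 mg reading is the least credible, since it conflicts with the stated 40 mg; it shows only that the 5 kg is loosely worded.

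A second reply is that the re-assay will reveal the dose. It would if the tomato mass per portion were fixed and recorded. No section does that, and no adjustment is tied to the result.

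A third is that little depends on it: section 8.1.2 lists no tablet-versus-soup endpoint, no statistical test is planned, and the 20 ml of oil written only for the soup already separates the arms. It is true that dose matching would not isolate food form. Secondary objective 1 and research question 2 nevertheless state the comparison at equivalent content, and a descriptive comparison is misled by unequal doses just as a formal one is.

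The plasma illustration rests on assumed dose relations and on equal uptake, which the Introduction's remarks on heat and oil make doubtful. It indicates scale only, and the conclusion does not depend on it.

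**Conclusion.** The protocol is wrong as written on this point. Prepared by the stated steps, 250 ml of soup delivers 21–22 mg, a little over half the stated 40 mg, and the tablets deliver 1.70–1.79 times as much. The result needs only the protocol's own tomato content and a density of 1.00–1.05 g/ml. It would not apply if the tomatoes are in fact reduced 1.8- to 1.9-fold, which may be intended but is not stated.

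The consequence falls on the tablet-versus-soup comparison. The effect on the primary objective is uncertain and probably small: in the illustration the lower dose still exceeds the 10% threshold at a base of 400 nmol/l and is borderline at 500 nmol/l.

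**What to change.** - Set the tomato mass per portion from the re-determined content: target mg divided by mg per g. At 8.4 mg per 100 g this is 446 g to match the tablets' actual 37.5 mg (the better target), or 476 g for 40 mg.
- State how that mass becomes a portion. Either reduce it to 250 ml by the same procedure for the batches of both periods, or serve it unreduced: about 425–446 ml for 37.5 mg (446/1.05 to 446/1.00), or 454–476 ml for 40 mg.
- State whether 5 kg is the total or the amount per batch.
- Record the tomato mass of every portion, and report the actual dose of each arm beside the curves.
- Optionally, assay the finished soup once per batch.

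The cost is a few sentences and a weighing record, with no extra participants or blood draws. The trade-off is a larger portion to eat or a standardised reduction step, whose extra heating may itself raise uptake according to the Introduction. The oil given only with the soup is a separate difference that this change does not remove.
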